11.4 Selection of Investigators and Training

Certified gastroenterologists will be considered for participation as investigators in this study. Physicians in training (residents, fellows) and physician assistants may assist the Study Investigator in any aspect of the procedure as per standard procedures and practices at his/her institution.

Each Investigator participating in the clinical trial and the associated clinical study staff will receive training on the clinical protocol. This includes training on AE reporting, electronic Case Report Form (eCRF) completion, and Good Clinical Practice (GCP), as well as the device and system (including procedural use, device characteristics, shelf life and storage requirements, warnings, and precautions).

12.0 Study Procedures

12.1 Clinical Laboratory Investigation

Samples for hematology, serum chemistry, urinalysis will be analyzed by the local laboratory at screening, at the 2, 6 and 12 months after the EndoZip procedure.

The panels of laboratory tests to be performed are showed below:

Hematology: red blood cells (RBC) and parameters (Hemoglobin, hematocrit) and reticulocyte count, white blood cells (WBC) and differential and platelets count.

- PTT, PT and INR will be done only at the screening visit.

Comprehensive Metabolic Panel (CMP) and urine analysis :Blood glucose, HbA1c, Calcium, Albumin, Total protein, Sodium, Potassium, Total CO₂, Chloride, ALP, ALT, AST, Bilirubin.

Urinalysis: Performed locally on freshly voided clean sample by dipstick for protein, glucose, blood, pH and ketones. If the dipstick finding are abnormal based on the provided Lab values or investigator's judgment, then a microscopic evaluation will be performed to assess the abnormal findings.

Lipid screen battery including Cholesterol level, HDL, LDL and Triglycerides.

	Title: Evaluation of EndoZip™ System (AS) in Obese Patients who failed to reduce weight with non-surgical weight-loss methods	
Document No: CL00003	Rev: 1.0	Page: 37 of 83

In addition, the following tests will be performed to evaluate patient health condition. These tests will be done only at the screening and at EndoZip procedure.

Endocrinology: a quantitative β-HCG blood test (R/o Pregnancy).

12- lead electrocardiogram (ECG): The test will be performed at screening, and at EndoZip procedure day. The following will be measured or calculated: Heart rate, PR, QRS, QT, QTc and rhythm. The investigator or qualified designee will review the ECG locally and assess the results as normal or abnormal (clinically significant or not clinically significant).

12.2 Physical Examination and Vital Signs

Physical examination will include an assessment of all the major body systems.

Vital signs will include blood pressure, heart rate, pulse and body temperature and will be taken in supine position after the patient has been resting for at least 5 minutes.

Physical examination and vital signs will be taken at all in-person visits during the study. The results will be documented in the eCRF.

12.3 Body Height, Weight and Waist Circumference

Height, Weight and Waist Circumference will be measured at all in-person visits. The results will be documented in the eCRF.

Waist Circumference Measuring instructions:

	Title: Evaluation of EndoZip™ System (AS) in Obese Patients who failed to reduce weight with non-surgical weight-loss methods		
Document No: CL00003	Rev: 1.0	Page:	38 of 83

To measure the waist, place a flexible tape measure between your bottom rib and your hip bone. The tape measure should be approximately in line with your belly button.

Take your waist measurement on a normal breath out

Don't pull or tuck in your stomach

Ensure the tape measure is level at the front and the back of your body

The tension of the tape should be such that the tape is held against the skin but not so tight as to cause an indentation in the skin

Waist Girth and Health Risk		
	Men	Women
Normal	78-94cm	64-80cm
Overweight (Elevated Risk)	94-102cm	80-88cm
Obese (High Risk)	>102cm	>88cm

12.4 Endoscopy Procedure

Endozip™ procedure is performed with concurrent endoscopy. The procedure will be done for safety and efficacy purposes. The stitches will be evaluated with respect to the order that they were applied per stomach location and their durability. Evaluated will be done via the endoscopy performed.

Endoscopy procedure will be performed at visit 4 (2 months after the procedure) and at visit 6 (6 months after the procedure). The results will be documented in the eCRF.

12.5 Assessment of Adherence

Patients will be instructed to follow post-procedure diet and physical activities, per Appendix A. Patients will be asked to record and provide their diet and their physical activities in the provided diary log at time of their scheduled follow-up visits (Diary log is provided in appendix C). Patients adherence to the instructed regime will be assessed in all follow-up visits. Adherence to the regime will be documented in the eCRF.

12.6 Quality of Life influence and Phycological Health Questionnaire

Quality of Life influence will be evaluated via IWQOL questionnaire, filled-out by the patients at screening, and at 2, 6 and 12 months after the procedure.

	Title: Evaluation of EndoZip™ System (AS) in Obese Patients who failed to reduce weight with non-surgical weight-loss methods		
Document No: CL00003	Rev: 1.0	Page:	39 of 83

Physiological health will be evaluated via PH-9 questionnaire, filled-out by the patients at screening visit and will support the patients' eligibility to the study.

The questionnaires will serve as source documents and will be transcribed into the study eCRF by Investigators or their designees.

12.7 Home Sleep Apnea Test (HSTS)

The test will be performed only for patients suffering from diagnosed obstructive sleep apnea. It will take place prior to the procedure, 2, 6 and 12 months after the procedure.

Obstructive sleep apnea (OSA) in this study is considered as a comorbidity if the hypopnea index, AHI, ≤ 15 events/hour. The purpose of the test is to evaluate if there is any improvement due to the Endozip™ procedure.

The following parameters will be measured:

1. Respiratory airflow
2. Respiratory effort
3. Oxygen saturation.

These parameters will be collected by the WatchPAT 200 (ITAMAR Medical –Israel) which is an FDA-approved portable diagnostic device that uniquely uses finger based physiology and innovative technology to enable simple and accurate Obstructive Sleep Apnea (OSA) testing.

For further instructions and guide: <https://www.youtube.com/watch?v=JqZczOBcVdk>

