9.2 Secondary endpoints

The following secondary endpoints will be evaluated:

1. Percent of excessive weight loss (%EWL) over 6 and 12 months.
2. Reduction of weight and waist circumference over 6 and 12 months.
3. Impact of EndoZip procedure on gastric motility at 6 months.
4. Changes in Weight-related Quality of Life (IWQOL) Questionnaire scores at 6 and 12 months.
5. Time analysis including procedure duration, anesthesia duration, patient recovery duration.
6. Change in comorbid conditions over 12 months evaluated by:
 - a. Blood pressure
 - b. Glucose, HbA1c
 - c. Lipid levels (Total Cholesterol, LDL-C, HDL-C, and triglycerides)
 - d. Sleep Apnea test
7. Physicians' satisfaction based on a questionnaire

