13.0 Study Schedule and Activities

13.1 Visit 1 - Screening and Informed Consent

A screening/baseline will be performed prior to the scheduled EndoZip procedure to assess preoperative eligibility. The patient clinical assessment includes few tests, thus it may be done in few days.

At the screening visit, patients will be approached to obtain written informed consent prior to any study specific procedures being performed. The purpose of the study and the benefits and risks of the procedures will be explained to the patient and the consent process must be documented accordingly in the medical record. Patients who agree to study participation must sign an IEC-approved ICF. Patients will be informed that their participation in this study is voluntary and they may refuse to participate or discontinue from the study at any time. Patients will be given the opportunity to ask the investigator questions so that they are adequately informed about the research. A copy of the signed informed consent must be provided to the patient and the informed consent process will be documented in source documents.

If new information becomes available that may affect a patient's decision to continue to take part in the study, this information will be discussed with the patient by the investigator.

An identifier will be assigned to each participant signing the informed consent form. This identifier will be assigned manually, in a sequential order, in the eCRF. Numbers of patients whose participation in the study is terminated prior to procedure may not be reassigned.

All patients that are considered to have comorbidities must have definite diagnosis previously to the screening visit (by blood tests and/or imaging).

The following assessments will be performed prior to the scheduled procedure and the results recorded on the appropriate patient eCRFs: Verification of eligibility Criteria:

- Assessment of demography characteristics
- Assessment of surgical and medical history (prior abdominal surgery, GI symptoms), Obesity History
- Assessment of general medical history including use of concomitant medication

	
Title: Evaluation of EndoZip™ System (AS) in Obese Patients who failed to reduce weight with non-surgical weight-loss methods
		
Document No: CL00003	Rev: 1.0	Page:	42 of 83

- Patient clinical condition will be assessed based on the followings:
 - Physical examination

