14.6 Secondary Endpoints Analysis

Excess Weight Loss % (EWL%)

EWL% of patients at 1, 2, 6 and 12 month(s) by study group will be summarized with descriptive statistics with 95% confidence intervals.

The percent excess weight loss (%EWL) will be calculated as $(\text{Weight(BL)} - \text{Weight(Visit)}) / \text{ExcessWeight(BL)}$, where ExcessWeight(BL) is calculated as difference between the patient's baseline weight in kilograms and the kilograms at which the patient's BMI would be 25.

Change of Weight and Waist Circumference Over 12 Months from Baseline

Change from baseline in BMI at 1, 2, 6 and 12 month(s) by study group will be summarized with descriptive statistics with 95% confidence intervals.

Changes in Weight-related Quality of Life (IWQOL) Questionnaire at 12 months

IWQOL questionnaire records will be summarized by study groups will be summarized with descriptive statistics with 95% confidence intervals.

Time analysis

Time analysis including procedure duration, anesthesia duration, patient recovery duration will be evaluated and will be summarized with descriptive statistics with 95% confidence intervals.

Change in Comorbid Conditions

Clinically significant changes at 6 and 12 months in fasting plasma glucose and HbA1c concentrations, change in systolic and diastolic blood pressure, changes in plasma total cholesterol, low-density lipoprotein cholesterol and triglyceride concentrations, will be evaluated and will be summarized with descriptive statistics with 95% confidence intervals

Percentage of patients who had clinically significant change will be provided with 95% confidence interval.

Usability and Physicians' satisfaction

Physicians' satisfaction will be evaluated by a questionnaire will be summarized with descriptive statistics with 95% confidence intervals.

	Title: Evaluation of EndoZip™ System (AS) in Obese Patients who failed to reduce weight with non-surgical weight-loss methods		
Document No: CL00003	Rev: 1.0	Page:	56 of 83

The physicians will be asked to fill-in a dedicated questionnaire to include their feedback on the procedure.

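### Section 12.7 counts sleep apnea as a comorbidity when AHI is at or below 15, the wrong direction for an event rate, and no analysis text settles how endpoint 6d is scored

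*Combined protocol and SAP*

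**What the plan says.** Section 12.7 (Home Sleep Apnea Test) contains four relevant statements:

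- Who is tested: "The test will be performed only for patients suffering from diagnosed obstructive sleep apnea". No AHI limit is attached.
- When: "It will take place prior to the procedure, 2, 6 and 12 months after the procedure".
- The comorbidity rule: OSA "is considered as a comorbidity if the hypopnea index, AHI, ≤ 15 events/hour".
- Why: "The purpose of the test is to evaluate if there is any improvement due to the Endozip™ procedure".

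The section then lists three measured parameters: airflow, respiratory effort and oxygen saturation. AHI is not on that list.

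Section 9.2 makes sleep apnea item d of secondary endpoint 6, introduced as "Change in comorbid conditions over 12 months evaluated by". Items a to c are blood pressure, glucose with HbA1c, and lipids.

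Section 13.1 adds that "All patients that are considered to have comorbidities must have definite diagnosis previously to the screening visit".

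The analysis of comorbid conditions in section 14.6 begins "Clinically significant changes at 6 and 12 months in fasting plasma glucose and HbA1c concentrations, change in systolic and diastolic blood pressure" and goes on to lipids. Sleep apnea does not appear there.

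**The concern.** The unit in section 12.7 is events per hour, so a larger value means more disease. A rule that grants the comorbidity at low values and withholds it at high values runs against the measure, and against a test whose purpose is to show improvement.

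The documents contain no other numeric definition of OSA, and section 14.6 gives no sleep-apnea analysis that would show the analyst what to do instead. An analyst who takes 12.7 literally could score endpoint 6d with the wrong sign. An analyst who uses the rule to choose a baseline subset could set aside the patients with the most events.

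**Working it through.** The plan gives no AHI data and no figure to reproduce. The check is therefore logical: apply the rule as written and see what it does.

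**Rule (section 12.7).** Label = comorbidity if AHI ≤ 15; otherwise no label.

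**Is the sign a reading artefact?** The BMI criterion in section 11.1 shows both ≥ 30 and ≤ 40 correctly, so both symbols survive in this text. A misread of this one sign cannot be wholly excluded, but nothing points to it.

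**Is it a deliberate entry cap?** No criterion in sections 11.1 or 11.2 limits AHI, and 12.7 tests all patients with diagnosed OSA.

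**Use 1: the rule is applied at baseline and again at follow-up.** The AHI values below are assumed.

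| Baseline → follow-up | Direction | Label before | Label after |
|---|---|---|---|
| 30 → 10 | better | no | yes |
| 40 → 30 | better | no | no |
| 12 → 5 | better | yes | yes |
| 12 → 20 | worse | yes | no |

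The same can be counted over all whole-number AHI pairs from 0 to 60 (61 values):

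- Improving pairs: 61 × 60 / 2 = 1830.
- Improving pairs that cross the cut-off: 45 baseline values (16 to 60) × 16 follow-up values (0 to 15) = 720. All 720 gain the label.
- Improving pairs that lose the label: 0.
- Improving pairs whose label does not change: 1830 − 720 = 1110, or 61%.
- By symmetry, 720 worsening pairs lose the label and 0 gain it.

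Every crossing of 15 is therefore scored in the wrong direction, and no improvement can appear as resolution. The grid describes the rule. It does not predict what share of patients would cross.

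A small example, also with assumed values: baseline AHI of 8, 12, 20, 30 and 45 gives 2 of 5 with the comorbidity. If the last three fall to 10 and the others stay put, the count becomes 5 of 5.

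**Use 2: the rule is applied at baseline only.** In the same example the label covers the patients at 8 and 12 and omits those at 20, 30 and 45. All five would still be tested at every scheduled time, so the data would exist; only the labelled subset would be wrong.

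**Use 3: endpoint 6d is analysed as change in the measured AHI.** The label plays no part and the result is unaffected. Nothing in section 14.6 says that this is the plan.

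**The case against.** The strongest reply is that the consequences depend on a use of the rule that the plan never states. No section says that the label is reapplied at follow-up, or that 6d counts patients who meet it. Section 9.2 names the item as a test result, beside other measured quantities. Section 13.1 ties comorbidities to a diagnosis made before screening, which fits a baseline label. This stands, and it rules out several stronger readings that a reader might infer:

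- *Endpoint 6d runs backwards.* This holds only if the rule scores 6d. As written, 6d has no specified analysis at all.
- *Improvement is reported as new disease.* Only patients already diagnosed are tested, so none can become a new case. At most a label changes.
- *Patients with severe disease are dropped.* They are still tested at baseline and at 2, 6 and 12 months. Whether an analysis would exclude them is not stated.
- *Every classification is inverted.* This presumes that the intended rule is the mirror image at the same cut-off, which the documents do not show. Even with a mirrored rule that included 15, a patient at exactly 15 would carry the label under both.

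It is also fair to say that an index could be derived from the three listed signals, so the absence of AHI from that list is a minor gap.

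None of this rescues the sentence in 12.7. It still contradicts the purpose given immediately after it, and no other text corrects or explains it.

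**Conclusion.** The point holds in limited form. The AHI rule in section 12.7 is wrong as written: its direction is contrary to an event rate and to the stated purpose of the test. The harm to endpoint 6d is conditional. Used to score change, the rule gives the wrong sign to every crossing of 15. Used as a baseline label, it omits the patients with most events. A change in AHI itself would be unaffected, but section 14.6 does not specify one.

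The reach is small: one of four components of one of seven secondary endpoints, in an unstated subset of up to 45 patients, in a pilot whose analyses are mainly descriptive. No primary endpoint or eligibility criterion uses the cut-off. The conclusion rests on the printed sign being the one in the source document; the AHI values used above are illustrations only. The documents do not show whether the sign, the number or the role of the sentence is at fault.

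**What to change.** 1. **Section 12.7:** reconcile the AHI rule with the purpose of the test and with endpoint 6d. The sponsor should confirm both the sign and the cut-off, and state whether the rule is a baseline label or is reapplied at follow-up.
2. **Recorded data:** list AHI among the parameters taken from the WatchPAT tests already scheduled.
3. **Section 14.6:** add a sleep-apnea analysis for 6d as paired change in AHI from baseline to 2, 6 and 12 months, in all patients with diagnosed OSA, summarised descriptively with 95% confidence intervals as for the other secondary endpoints. The result then does not depend on the label.

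The cost is a corrected sentence, one analysis paragraph and, if AHI is not already captured, one eCRF field (the eCRF is not among the documents). No extra test or visit is needed.

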12.8 Gastric Emptying Breath Test (GEBT)

The Gastric Emptying Breath Test (GEBT), to be used with the GEBT test meal, is intended for use in the measurement of the rate of gastric emptying of solids and as an aid in the diagnosis of delayed

	Title: Evaluation of EndoZip™ System (AS) in Obese Patients who failed to reduce weight with non-surgical weight-loss methods		
Document No: CL00003	Rev: 1.0	Page:	40 of 83

gastric emptying. The test will be performed for all patients prior to the Endozip™ procedure and 6 months after the procedure.

GEBT is a non-radioactive test that utilizes carbon-13 (13C). Labeling with 13C stable isotope is essentially safe, as 1.1% of our bodies, and of the food we eat, consists of 13C; the remaining 98.9% consists of 12C. The GEBT measures the rate of gastric emptying of solids and aids in the diagnosis of gastroparesis. The test system utilizes a gas isotope ratio mass spectrometer for the measurement of the ratio of 13CO₂ to 12CO₂ in breath samples. In a clinical trial comparing the GEBT and scintigraphy, the GEBT was shown to be comparable to scintigraphy. The GEBT is shown in Figure 2.

Contraindications to use of the GEBT:

- Individuals with known hypersensitivity to Spirulina, egg, milk or wheat allergens should avoid the GEBT.
- Because the GEBT is an indirect multi-compartmental method of measuring gastric emptying, GEBT results may be inaccurate in individuals compromised with significant small bowel, pancreatic, liver and/or lung disease. Consequently, GEBT should not be administered to patients with pulmonary dysfunction (e.g. COPD) and/or small bowel malabsorption.

The GEBT procedure flow chart is presented in Figure 3.

Figure 2 - GEBT kit for gastric emptying testing

[figure not shown]

Figure 3 – GEBT Procedure Flow chart

	Title: Evaluation of EndoZip™ System (AS) in Obese Patients who failed to reduce weight with non-surgical weight-loss methods		
Document No: CL00003	Rev: 1.0	Page:	41 of 83

12.1 Usability Assessment

Usability will be evaluated by a questionnaire. The physicians who will conduct the EndoZip procedure will fill-out a dedicated questionnaire specified in Appendix B. The Physician feedback will be documented in the eCRF.

13.0 Study Schedule and Activities

13.1 Visit 1 - Screening and Informed Consent

A screening/baseline will be performed prior to the scheduled EndoZip procedure to assess preoperative eligibility. The patient clinical assessment includes few tests, thus it may be done in few days.

At the screening visit, patients will be approached to obtain written informed consent prior to any study specific procedures being performed. The purpose of the study and the benefits and risks of the procedures will be explained to the patient and the consent process must be documented accordingly in the medical record. Patients who agree to study participation must sign an IEC-approved ICF. Patients will be informed that their participation in this study is voluntary and they may refuse to participate or discontinue from the study at any time. Patients will be given the opportunity to ask the investigator questions so that they are adequately informed about the research. A copy of the signed informed consent must be provided to the patient and the informed consent process will be documented in source documents.

If new information becomes available that may affect a patient's decision to continue to take part in the study, this information will be discussed with the patient by the investigator.

An identifier will be assigned to each participant signing the informed consent form. This identifier will be assigned manually, in a sequential order, in the eCRF. Numbers of patients whose participation in the study is terminated prior to procedure may not be reassigned.

All patients that are considered to have comorbidities must have definite diagnosis previously to the screening visit (by blood tests and/or imaging).

The following assessments will be performed prior to the scheduled procedure and the results recorded on the appropriate patient eCRFs: Verification of eligibility Criteria:

- Assessment of demography characteristics
- Assessment of surgical and medical history (prior abdominal surgery, GI symptoms), Obesity History
- Assessment of general medical history including use of concomitant medication

	
Title: Evaluation of EndoZip™ System (AS) in Obese Patients who failed to reduce weight with non-surgical weight-loss methods
		
Document No: CL00003	Rev: 1.0	Page:	42 of 83

- Patient clinical condition will be assessed based on the followings:
 - Physical examination
 - Vital signs (blood pressure and heart rate - supine, pulse, body temperature, respiratory rate (RR) and SpO2)
 - Waist circumference, Height, Weight
 - Laboratory evaluations (Hematology, CBC with differential, PTT, PT and INR, Comprehensive Metabolic Panel (Kidney and liver functions – blood glucose, HbA1c, Urinalysis, TSH, fasting lipid panel)
 - Gastric Emptying Breath Test (GEBT)
 - Weight on Quality of Life (IWQOL) questionnaire
 - Psychological health questionnaire-9 (PHQ-9)
 - Patients with diagnosed Sleep Apnea disorder will undergo HSAT (home sleep apnea testing).

13.1.1 Recruitment visit:

Patients who are eligible for the study will be invited to participate in the study.

Patients who were found to be not eligible for the study following signature of the Informed Consent Form will be withdrawn from the study.

